2.3.2.9 Disease-specific survival

2.3.2.10 Overall Survival.

- 2.3.2.11 Patient reported Health-related quality of life as measured by the IPSS and EPIC-26 assessments (see Appendices B and C).
- 2.3.3 NCI CTCAE v4.03 toxicity criteria will be used to assess acute and late adverse events/toxicity endpoints (Appendix A). Disease specific endpoints will utilize a combination of laboratory values, multidisciplinary clinical decisions, radiographic imaging, functional imaging, and initiation of salvage therapy.

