7.0 HORMONE THERAPY

Other than androgen deprivation therapy, patients must not receive other cancer-directed therapy (including standard fractionated radiotherapy, chemotherapy, biological therapy, and surgery) while on-study except at disease progression.

Standard institutional practices for neoadjuvant/concurrent and adjuvant short-term (6 months) androgen deprivation hormonal therapy will be used with the salvage

radiotherapy regimen. When possible, radiotherapy will begin approximately 2 months after the start of hormonal therapy. Some patients may have received prior hormonal therapy, but still require 6 months with the trial.

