9.0 MEASUREMENT OF EFFECT

9.1 *Antitumor Effect- Solid Tumors*

9.1.1 Definitions:

Evaluable for toxicity: All patients will be evaluable for toxicity immediately following brachytherapy.

Evaluable for disease control assessment: All patients with at least 2 follow-up PSAs will be evaluable for disease control. After brachytherapy, these patients will have their disease status classified according to the definitions stated below.

Biochemical (PSA) recurrence (BR): Based on RTOG Phoenix definition: an increase of the PSA level at least 2 ng/ml greater than the minimum level after therapy (REF: phoenix paper)

All patients with BR should undergo at least MP-MRI of the prostate and bone scan. Biopsy of any suspicious lesions within the prostate gland on MP-MRI is encouraged.

Freedom from Biochemical (PSA) Recurrence (FFBR):

The time to PSA failure will be measured from the date of treatment to the date of a rise by 2 ng/mL or more above the nadir PSA. The time of failure will be the date of the first PSA that is 2 ng/mL or more above the lowest prior post-treatment PSA value. If the rise in PSA to $>$ nadir + 2 occurs during the first 36 months followed by a subsequent non-hormonal induced PSA decrease, patients will **not** be considered PSA failures.

As a benign “spike” or “bounce” in the PSA value has been described in as many as 35% of patients 12-36 months following brachytherapy, intervention for a PSA failure should be based on a positive prostate biopsy at least 24 months post-treatment and/or clinical evidence of distant relapse (i.e., bone scan, CT scan, etc).

Local Failure (LF): This rating will be assigned when there is biopsy-proven disease progression or recurrence at the lesion within the prostate treated with protocol therapy. Histologic criterion for local failure is the presence of prostatic carcinoma upon biopsy more than 2 years after the start of treatment. Residual carcinoma on biopsy should show minimal radiation effect and should be in clinical scenario of increasing PSA.

Local Control (LC): Absence of local failure. This will be assumed in patients with a controlled PSA and for those with PSA failure but no radiographic, clinical, or biopsy-proven disease at the lesion treated with protocol therapy.

Freedom from Local Failure (FFLF): The time to local progression will be measured from the date of treatment to the date of local failure.

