Elsewhere Prostate Failure (EPF): This rating will be assigned when there is biopsy-proven disease progression/recurrence at outside the lesion treated with protocol therapy but within the prostate or seminal vesicles.

Elsewhere Prostate Control (EPC): Absence of EPF. Will be assumed in patients with a controlled PSA and in patients with PSA failure but no radiographic, clinical, or biopsy-proven disease at the site treated with protocol therapy.

Freedom from Elsewhere Prostate Failure (FFEPF): The time to elsewhere prostate failure will be measured from the date of treatment to the date of EPF.

Regional Failure (RF): Visible disease on imaging that occurs in lymph nodes within the usual regional spread pattern of prostate cancer

Regional Control (RC): Absence of regional/nodal recurrence.

Freedom from Regional Failure (FFRF): The time to regional failure will be measured from the date of treatment to the date of RF.

Distant Metastasis (DM): Visible disease on imaging that occurs elsewhere in the body including non-regional lymph nodes.

Freedom from Distant Metastasis (FFDM): The time to distant metastasis will be measured as the date of treatment to the date of DM.

Freedom from hormone therapy (FFHT): The time from the date of treatment to first administration of androgen deprivation therapy

Disease-free Survival (DFS): Defined as the duration of time from the date of completion of treatment to either BR, LF, EPF, RF, DM, or death.

Cause-specific Survival (CSS): Defined as the duration of time from the date of completion of treatment to death from prostate cancer.

Overall Survival (OS): Defined as the duration of time from the date of completion of treatment until death from any cause.

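### Salvage hormone therapy started while PSA is below nadir + 2 is not an FFBR or DFS event in section 9.1.1, although section 2.3.3 says salvage therapy will feed the disease endpoints

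*Combined protocol and SAP*

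**What the plan says.** Section 2.3.3 states that the disease endpoints will draw on laboratory values, clinical decisions, "radiographic imaging, functional imaging, and initiation of salvage therapy".

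The definitions in section 9.1.1 do not carry the last item through:

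- Biochemical recurrence and FFBR depend on PSA alone, with failure dated at "the date of a rise by 2 ng/mL or more above the nadir PSA".
- DFS runs from the "date of completion of treatment to either BR, LF, EPF, RF, DM, or death".
- For Local Control the text says "This will be assumed in patients with a controlled PSA", and Elsewhere Prostate Control has a parallel rule. Both also assume control in men with PSA failure but no demonstrated lesion.
- Freedom from hormone therapy (FFHT) is the only definition that refers to a therapy start. It does not feed into FFBR or DFS.

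On treatment, section 7.0 specifies "short-term (6 months) androgen deprivation hormonal therapy", and section 7.2 also fixes the LHRH course at 6 months. Section 7.0 opens, however, with a restriction worded "Other than androgen deprivation therapy, patients must not receive other cancer-directed therapy", and nothing in that sentence confines the exemption to the protocol course.

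In the section 8.3 schedule, bone scan and multi-parametric MRI appear pre-study and at biochemical recurrence only, and PET/CT appears pre-study only. Section 12.3 has no rule for censoring or otherwise handling non-protocol ADT.

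**The concern.** ADT lowers PSA. If it is started because PSA is climbing but has not yet reached nadir + 2, the threshold that defines failure may not be crossed for a long time. The man has in practice left the salvage-radiotherapy strategy, yet the FFBR analysis carries him as failure-free.

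The effect passes to DFS through the schedule. Reaching biochemical recurrence is what triggers the scheduled imaging. Without that trigger, regional, distant, local and elsewhere-prostate failures are less likely to be found, and death is the only DFS component that does not depend on a work-up.

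The authors evidently recognise that hormones mask PSA. The bounce exception cancels a failure only when it is "followed by a subsequent non-hormonal induced PSA decrease". That safeguard works after nadir + 2 has been passed; there is no counterpart before it.

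This matters because section 1.5 says the data are meant to lead to a phase III comparison with palliative hormonal therapy. A man already moved to that kind of treatment could be reported as biochemically controlled and disease-free on the radiotherapy regimen.

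**Working it through.** **1. The plan's own figures.** The only design calculation is the toxicity design in section 12.2: stop if 2 or more of 7 men have toxicity; reject the null if 4 or fewer of 24 do (more than 19 non-toxic).

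- Early stopping at p = 0.33: 1 − [0.67^7 + 7 × 0.33 × 0.67^6] = 0.730 (stated 73%).
- P(reject) = Σ over x = 0, 1 of P(Bin(7, p) = x) × P(Bin(17, p) ≤ 4 − x). At p = 0.33 this is 0.0462 (stated .046); at p = 0.10 it is 0.809 (stated 81%).

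These reproduce, and none of them uses FFBR or DFS. The point below does not touch them.

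**2. The definitions applied to one man.** Suppose he completes protocol treatment, his PSA later rises by less than 2 ng/mL above nadir, and non-protocol ADT is started for that rise alone.

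| Endpoint (9.1.1) | Event at ADT start? | Reason |
|---|---|---|
| FFBR | No | Threshold not reached; no therapy component |
| DFS | No, unless another component is found | Therapy start not listed; imaging not triggered |
| LC, EPC | Control assumed while PSA is controlled | No distinction by what controls the PSA |
| FFHT | Unclear | Counts first ADT without separating protocol from salvage ADT |

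Section 2.3.3 says salvage therapy will be used; of these definitions, only FFHT uses a therapy start at all.

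**3. Size per man.** With n men evaluable and followed to the time point, moving one man from failure-free to failed changes the proportion by 1/n. For n = 24 this is 1/24 = 4.2 points. Section 9.1.1 requires at least 2 follow-up PSAs for evaluability, so n may be smaller and the step larger.

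**4. Illustration (assumed counts).** Take 24 evaluable men followed to 24 months, the time point named in section 12.3. Assume e = 6 reach nadir + 2, and k others start salvage ADT before reaching it.

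- As written: 1 − e/24.
- ADT start counted as an event: 1 − (e + k)/24.
- Censored at ADT start, assuming all k starts at 12 months and all PSA events later (Kaplan-Meier): 1 − e/(24 − k).

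| k | As written | Counted as event | Censored |
|---|---|---|---|
| 2 | 18/24 = 75.0% | 16/24 = 66.7% | 1 − 6/22 = 72.7% |
| 4 | 18/24 = 75.0% | 14/24 = 58.3% | 1 − 6/20 = 70.0% |

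Over k = 1 to 4, the gap between the first two methods is 4.2 to 16.7 points (1/24 to 4/24). The documents give neither e nor k.

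**The case against.** The strongest reply is that the protocol leaves little room for this to happen. The LHRH course is fixed at 6 months, section 13.7 requires the study to be run as described, and section 13.7.2 requires prior approval for planned deviations. Section 9.1.1 also advises that intervention for a PSA failure rest on a positive biopsy at 24 months or later and/or clinical evidence of distant relapse. Where that advice is followed, the biopsy or scan will often itself be a DFS event.

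Much of this stands, and it rules out several stronger readings that a reader might infer:

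- *That early salvage ADT, or extending the course, is permitted.* No section authorises ADT for a sub-threshold PSA, and extension departs from the stated 6 months. The exemption in section 7.0 can be read as covering protocol ADT only. The gap does not depend on permission, though: ADT given as a deviation would equally have no endpoint rule. Section 7.0 also allows other therapy at disease progression, which that section does not tie to nadir + 2.
- *That the failure is never recorded.* PSA failure is judged against the lowest prior post-treatment value, so a later rise on or after ADT can still count, and regional failure, distant metastasis and death remain DFS events. The event is delayed or masked.
- *That ADT suppression is what produces the LC and EPC credit.* Both already assume control despite PSA failure when no lesion is shown. Suppression matters there only if it prevents a work-up that would have been positive.
- *That every such man is a hidden relapse.* Section 9.1.1 cites a benign PSA bounce in as many as 35% of patients, so some ADT could be started for a rise that is not recurrence.

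What survives is the mismatch between sections 2.3.3 and 9.1.1, confined to ADT started on a sub-threshold PSA without other evidence of failure. The advice on intervention is guidance about a PSA failure and does not address that case.

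**Conclusion.** The point holds in this limited form. Section 2.3.3 promises to use the start of salvage therapy, and the FFBR and DFS definitions do not. A relapsing man started on non-protocol ADT below nadir + 2 has no FFBR event at that time and probably no DFS event while PSA is suppressed, so both estimates lean in the favourable direction.

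The size is 4.2 points per such man if all 24 are evaluable and his failure would otherwise fall within the reporting window. The total is unknown because the documents give no frequency of early salvage ADT. If no man is treated this way, there is no effect.

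The affected endpoints are secondary and descriptive. A reader might infer that the trial's main conclusion is at risk; it is not, since the toxicity endpoint and its operating characteristics are unchanged. The correction is still worth making because the efficacy figures are intended to inform a phase III trial.

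**What to change.** 1. In section 9.1.1, count the start of non-protocol cancer-directed therapy, including ADT, given for suspected or confirmed recurrence as an FFBR and DFS event on its start date if no earlier event has occurred. Exclude the protocol ADT course and its administrative overrun, so that a late-finishing course is not scored as failure.
2. Record the start date of, and reason for, any such therapy.
3. Add a sensitivity analysis that censors at that date. Such censoring is likely to be informative, so report it beside the main estimate and not in its place.
4. Report LC and EPC with men on salvage ADT identified separately, not assumed controlled on PSA alone.
5. Reconcile the ADT exemption in section 7.0 with the 6-month duration in sections 7.0 and 7.2. This is a matter of consistency only; the statistical text need not say when ADT may be given.

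**Cost.** Wording changes in sections 7.0 and 9.1.1, and a small data-collection addition. Section 8.3 schedules a Medication Assessment, but the documents do not state that the date or reason for salvage ADT is captured there. FFHT already needs an ADT date, so the extra burden is small. FFBR and DFS may look slightly less favourable, and a man treated for a benign PSA rise may be counted as an event; the sensitivity analysis shows how much that matters.

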12.3 Data Analyses Plans

For this single group trial, summary frequencies and statistics will be provided for all relevant patient characteristics and clinical measures, including demographics (e.g., age, cancer stage, educational attainment, etc) as well as clinical outcomes (e.g., laboratory monitoring, adverse event monitoring, etc.). These include valid counts with percentages for categorical and ordinal variables as well as median with interquartile range or mean with standard deviation or standard error for continuous variables.

For the primary aim, a one-tailed one-sample test for proportions will be used to test whether the observed toxicity rate is lower than the hypothesized toxicity rate. For relapse-free survival, death will *not* be considered a competing event.

Instead, a two-sided one-sample log-rank test will be used to estimate the probability of being relapse free 24 months following treatment.

The instantaneous risk of relapse or death may be estimated as a function of age, cancer stage, and other covariates using semi-nonparametric Cox proportional hazards models. For these models, the number of covariates used for the adjustment will be determined by the number of events. Approximately one predictor for every 10 relapse or mortality events may be used to determine adjusted survival probabilities as described by Peduzzi et al.²⁴ For all Cox proportional hazards models, the proportional hazards assumption will be evaluated using Martingale residuals as described by Lin, Wei, and Ying.²⁵ If the proportional hazards assumption is violated, parametric accelerated failure time models may be used assuming the true underlying hazard distribution is identified.

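### The PSA bounce exception in Section 9.1.1 cancels a biochemical failure after any later non-hormonal PSA fall, so true failures can drop out of FFBR

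*Combined protocol and SAP*

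**What the plan says.** All the relevant definitions are in Section 9.1.1 of the combined protocol and SAP.

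- **BR** is the Phoenix definition: "an increase of the PSA level at least 2 ng/ml greater than the minimum level after therapy". No bounce exception is attached to it.
- **FFBR** uses the same threshold and fixes the date: "The time of failure will be the date of the first PSA that is 2 ng/mL or more above the lowest prior post-treatment PSA value". It then adds the exception: a rise above nadir + 2 that "occurs during the first 36 months followed by a subsequent non-hormonal induced PSA decrease" does not make the patient a PSA failure.
- **Reason given.** Benign bounce "has been described in as many as 35% of patients 12-36 months following brachytherapy". The same paragraph adds that "intervention for a PSA failure should be based on a positive prostate biopsy at least 24 months post-treatment and/or clinical evidence of distant relapse".
- **DFS** counts BR, local, elsewhere-prostate and regional failure, distant metastasis and death.

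Section 7.0 governs other treatment: "patients must not receive other cancer-directed therapy (including standard fractionated radiotherapy, chemotherapy, biological therapy, and surgery) while on-study except at disease progression".

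The Section 8.3 table schedules PSA at months 3, 6 and 12 and then six-monthly, with a footnote ending follow-up at progression, death or the end of the follow-up period.

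Section 12.2 lists FFBR among outcomes to be described, with no power or target rate. Section 12.3 plans a one-sample log-rank test for relapse-free survival, to "estimate the probability of being relapse free 24 months following treatment".

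**The concern.** Allowing for bounce after brachytherapy is conventional, and the protocol gives its reason. The difficulty is that the operative sentence describes any dip, whereas a bounce is a rise that resolves. It lacks three things:

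1. **Size.** A fall within ordinary measurement variation qualifies, even with PSA still well above nadir + 2.
2. **Cause.** Only hormone-induced falls are excluded. A fall produced by the non-hormonal treatments that Section 7.0 allows at progression meets the wording, so treating a failure can delete it.
3. **A second rise.** The text does not say whether a patient cleared as a bounce who reaches nadir + 2 again is then a failure, or on what date.

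There is also a mismatch. BR carries no exception and feeds DFS; FFBR carries it. One PSA series can therefore be a BR event in DFS and not a failure in FFBR.

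Section 1.5 says the data are meant to support a phase III trial against palliative hormonal therapy. A disease-control rate that includes cancelled true failures would be hard to interpret for that purpose.

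**Working it through.** The plan states no expected FFBR rate, so there is no figure to reproduce. Three checks follow.

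**1. Literal reading.** Take PSA 0.5 (nadir), 4.0, 3.9 ng/mL within 36 months. The threshold is 0.5 + 2 = 2.5. The second value is a failure (4.0 ≥ 2.5). The third is lower than the second, so the exception applies although 3.9 is still 1.4 above the threshold. Under BR the same series is an event.

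**2. Effect of one reclassification.** With n = 24 (Section 12.2), crude FFBR = 1 − failures/24, so each cancelled failure adds 1/24 = 4.2 points. Assume for illustration 8 true failures:

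| Cancelled | FFBR |
|---|---|
| 0 | 1 − 8/24 = 66.7% |
| 1 | 1 − 7/24 = 70.8% |
| 2 | 1 − 6/24 = 75.0% |
| 4 | 1 − 4/24 = 83.3% |

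**3. How often noise alone cancels a true failure.** The documents give no PSA kinetics, so these inputs are assumptions: PSA 1.0 ng/mL at month 6, exponential growth from then, log-normal variation, and visits at months 3, 6, 12 and then every six months to month 60. The table gives the simulated share of true failures triggered by month 36 that have any later PSA below the triggering value.

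| Doubling time | CV | Share cancelled |
|---|---|---|
| 3–6 months | 10–20% | 0–1% |
| 9 months | 20% | 8% |
| 12 months | 20% | 18% |
| 12 months | 30% | 38% |
| 18 months | 20% | 44% |

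**How far slow risers matter.** With nadir N at month 6 and doubling time D, PSA reaches nadir + 2 by month 24 if N × 2^(18/D) ≥ N + 2, that is, N ≥ 2/(2^(18/D) − 1).

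- D = 24 months: 2^0.75 = 1.68, so N ≥ 2/0.68 = 2.9 ng/mL.
- D = 18 months: N ≥ 2/(2 − 1) = 2.0 ng/mL.
- N = 0.5: 2^(18/D) must be at least 5, so D ≤ 7.75 months.

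The chance that one six-monthly value falls below the one before is Φ(−(6 ln 2/D)/(σ√2)), with σ² = ln(1 + CV²). At CV 15%, σ = 0.149. For D = 7.75 this is Φ(−2.54) = 0.55%, or about 1.1% over two visits. For D = 24 it is Φ(−0.82) = 21%, or about 40% over two visits. The high figure therefore belongs to patients who fail by month 24 only from a nadir near 3 ng/mL.

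**Would requiring a return below nadir + 2 help?** Starting from 1.0 ng/mL with CV 15%, and counting the two visits after the first crossing, any drop occurs in about 13% of steady risers at a 12-month doubling time, against about 1% who fall back below nadir + 2. At 18 months the figures are about 40% against 8–9%. Most of the noise effect goes, and a bounce that truly resolves remains exempt.

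**The case against.** The best defence is that the rule serves a sound purpose. The protocol cites bounce in up to 35% of patients, and plain nadir + 2 would count bounces that exceed 2 ng/mL as failures. Relative to plain nadir + 2 the exception can only raise FFBR. Relative to true recurrence the net direction depends on how many real bounces it removes, which the documents do not give. That stands: upward bias is possible, not shown.

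A reader might infer several stronger points, which the text does not support:

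- **That salvage treatment in general erases failures.** Hormone-induced falls do not trigger the exception, and Section 1.1 calls palliative androgen deprivation the primary treatment for nodal recurrence after radiotherapy. The gap covers non-hormonal salvage only. Section 9.1.1 narrows it further by tying intervention to a biopsy at 24 months or later and/or distant relapse. It does not close it: distant relapse has no time limit, and biopsy-led treatment can fall in months 24–36.
- **That DFS is inflated too.** DFS uses BR, which has no exception. The defect there is inconsistency.
- **That the 24-month relapse-free analysis sits inside the 36-month window.** Relapse-free survival is listed separately from FFBR in Section 12.2, is never defined, and is not tied to the exception.
- **That a cleared patient can never fail later.** The text is silent on a second rise.

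Two further limits are fair. The Section 8.3 footnote may stop scheduled PSA at progression, so values after salvage may not exist. And the fix also classifies a rise by later data; what it changes is how strong those data must be.

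**Conclusion.** The point holds in a limited form. As written, the FFBR exception lets any later non-hormonal PSA fall cancel a failure in the first 36 months, including a trivial fall above the threshold or a fall after non-hormonal salvage. Each true failure so cancelled adds 4.2 points to crude FFBR in 24 patients. How many would be cancelled is not known. On the assumed kinetics, noise cancels 0–1% of failures with doubling times of 3–6 months at CV 10–20%, and 18–44% with doubling times of 12–18 months at CV 20%.

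It would go too far to say that FFBR is biased upward against true recurrence, since correctly removed bounces pull the other way. The BR/FFBR mismatch is certain from the text and needs no assumption.

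FFBR is secondary and descriptive. The primary toxicity test, the stage-one stopping rule and the sample size are untouched. The definition should be corrected, but it does not threaten the trial's main conclusion.

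**What to change.** Change the endpoint definition in Section 9.1.1; no treatment rule needs to change.

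1. Count a rise as a bounce only if PSA later returns below nadir + 2 with no anticancer therapy of any kind between the rise and the fall. Otherwise the failure stands at the date of the first qualifying PSA.
2. If a patient cleared as a bounce reaches nadir + 2 again, count a failure at that later date.
3. Use one definition for BR, FFBR and DFS.
4. Report FFBR under plain nadir + 2, with no exception, as a sensitivity analysis.
5. State whether PSA collection continues after a first value at nadir + 2, since any bounce rule needs later values and the Section 8.3 footnote leaves this open.

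The cost is a few sentences and one extra analysis of the PSA series the plan already schedules. The small downside is that a few more patients will be counted as failures.

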8.1.11 Labs

AST, ALT, Alkaline Phosphatase, and any labs required for the brachytherapy procedure as part of usual care.

8.2 *Follow-up Procedures*

Patients will be followed as described in Section 8.3.

8.3 *Study Parameters*

	Pre-study	Start of EBRT	Week 4 post-treatment	Month 3 & 6	Month 12	Follow-up Q 6 months*	Time of Biochemical Recurrence
Informed Consent	X						
History and PE, including DRE	X		X	X	X	X	
Medication Assessment	X		X	X	X	X	
Performance Status	X		X	X	X	X	
Toxicity Assessment			X	X	X	X	
PSA	X			X	X	X	
Bone scan	X						X
MP-MRI	X						X¥
PET/CT	X						
IPSS score	X		X	X	X	X	
EPIC-26	X		X	X	X	X	
AST/ALT/ALK PHOS	X	X					

* Until disease progression, death, or follow up period is complete

¥If MP-MRI reveals any suspicious lesions, then biopsy is encouraged.

DRE – Digital Rectal Exam

PE – Physical Exam

MP – Multi-parametric

EBRT – External Beam Radiotherapy

8.4 *Removal of Subjects from Study*

Patients can be taken off the study treatment and/or study at any time at their own request, or they may be withdrawn at the discretion of the investigator for safety, behavioral, or administrative reasons. The reason(s) for discontinuation will be documented and may include:

- 8.4.1 Patient voluntarily withdraws prior to treatment;
- 8.4.2 Patient withdraws consent (termination of treatment and follow-up);
- 8.4.3 Patient is unable to comply with protocol requirements;
- 8.4.4 Patient develops interval co-morbidity that makes continuation in the protocol unsafe;
- 8.4.5 Treating physician(s) judge(s) the study would not be in the patient's best interest;
- 8.4.6 Development of second malignancy (except for basal cell carcinoma or squamous cell carcinoma of the skin) that requires treatment, which would interfere with this study;
- 8.4.7 If a research subject cannot be located to document survival after a period of 2 years; the subject may be considered "lost to follow-up". All attempts to contact the subject during the two years must be documented and approved by the Data Monitoring Committee.

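### Local and elsewhere-prostate failure count only when biopsy-proven, but biopsy is only encouraged, so unbiopsied recurrences drop out of both freedom-from-failure curves

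*Combined protocol and SAP*

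**What the plan says.** **Failure.** Section 9.1.1 assigns local failure (LF) as follows: "This rating will be assigned when there is biopsy-proven disease progression or recurrence at the lesion within the prostate treated with protocol therapy". It adds a histologic criterion, the "presence of prostatic carcinoma upon biopsy more than 2 years after the start of treatment". Elsewhere-prostate failure (EPF) requires "biopsy-proven disease progression/recurrence at outside the lesion treated with protocol therapy but within the prostate or seminal vesicles", with no time limit. Freedom from local failure (FFLF) and freedom from elsewhere-prostate failure (FFEPF) run from treatment to the dates of those events.

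**Work-up at PSA failure.** On imaging, Section 9.1.1 says "All patients with BR should undergo at least MP-MRI of the prostate and bone scan". On biopsy it says only "Biopsy of any suspicious lesions within the prostate gland on MP-MRI is encouraged", and the footnote to the Section 8.3 table repeats this: "If MP-MRI reveals any suspicious lesions, then biopsy is encouraged". The text on PSA bounce adds that "intervention for a PSA failure should be based on a positive prostate biopsy at least 24 months post-treatment and/or clinical evidence of distant relapse".

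**Control.** Local control (LC) is first defined as not having LF. After PSA failure it is then presumed only when imaging, clinical findings and biopsy all show nothing at the treated lesion. Elsewhere-prostate control (EPC) has the same second sentence, and that sentence also refers to the treated site.

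**Other endpoints.** Section 2.3.3 says the disease endpoints draw on imaging, multidisciplinary decisions and the start of salvage therapy. Regional failure and distant metastasis need only visible disease on imaging.

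**The concern.** The LF and EPF events depend on a procedure that the protocol does not require. No rule covers a man with PSA failure and a suspicious MRI lesion in the prostate who is not biopsied. His disease may be real, but the definitions give him no LF or EPF event.

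Two things are at stake. First, FFLF and FFEPF would partly measure how often men are re-biopsied, and would read too favourably wherever an unbiopsied lesion is a true recurrence. Second, two analysts could classify the same man differently for local control. Local control is named in secondary objective 2.2.2, and Section 1.5 says the data are meant to inform a phase III trial. In-prostate failure would also be held to a stricter standard than nodal or distant failure, which distorts a description of where men relapse.

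**Working it through.** **1. Classify one man under each definition.** He has PSA failure, a suspicious prostate lesion on MRI and no biopsy.

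| Endpoint | Test in the text | Result |
|---|---|---|
| FFLF | LF needs biopsy proof | no event |
| FFEPF | EPF needs biopsy proof | no event |
| LC, first sentence | LF absent | controlled |
| LC, second sentence (lesion at treated site) | no radiographic disease at the treated lesion | control not presumed |
| EPC, second sentence (lesion only elsewhere in the gland) | no disease at the *treated* site | control presumed despite the lesion |
| Disease-free survival | biochemical recurrence is enough | event |
| FFBR (freedom from biochemical recurrence) | PSA at least 2 ng/mL above nadir | event, unless the bounce exception applies |

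**2. Weight of one man.** 1/24 = 0.042, or about 4 percentage points.

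**3. Size.** The documents give no figure for FFLF, FFEPF or biopsy uptake, so there is no stated value to reproduce. What follows is an illustration only.

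- *B*, 5-year PSA failure: 1 − 0.689 = 31.1% and 1 − 0.51 = 49%, from the two salvage HDR series in the background.
- *L*, local share of PSA failures: up to 55% in the background; the low end of 25% is my assumption.
- *u*, share of true failures biopsied: not given, so 0% to 100%.
- True failure F = B × L. If unbiopsied men stay at risk, apparent freedom = 1 − F × u.

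| Case | F | True freedom | True events in 24 | Apparent at u = 50% | Gap |
|---|---|---|---|---|---|
| Low | 0.311 × 0.25 = 0.078 | 92.2% | 1.9 | 96.1% | 3.9 points |
| High | 0.49 × 0.55 = 0.270 | 73.0% | 6.5 | 86.5% | 13.5 points |

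At u = 0% apparent freedom is 100%; at u = 100% the gap is zero. The table puts all in-prostate recurrences into one curve. A man with a lesion at one site belongs to one curve only, so the gap is shared between FFLF and FFEPF.

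**4. Does censoring help?** A Kaplan-Meier simulation used exponential failure times over 60 months, uptake of 50% unrelated to timing, and PSA failure taken to coincide with local failure. F was 17% (0.311 × 0.55) and 27% (0.49 × 0.55).

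| True freedom | Unbiopsied men kept at risk | Censored at PSA failure |
|---|---|---|
| 83% | 91.6% | 91.2% |
| 73% | 86.5% | 85.5% |

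The closed forms agree to 0.1 point. Kept at risk, 1 − F × u gives 91.5% and 86.5%. Censored, (1 − F)^u gives 0.83^0.5 = 91.1% and 0.73^0.5 = 85.4%. Censoring removes at most 1 point of the gap, because the men censored are those who have just failed.

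**5. Primary aim.** The two-stage rule reproduces: type I error 0.0462 (stated .046), power 0.809 (stated 81%) and early stopping 0.730 at a 33% toxicity rate (stated 73%). It uses toxicity counts only, so none of it depends on this point.

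**The case against.** Requiring tissue is a defensible choice. After radiation an MRI lesion may not be recurrence, and the LF text asks for minimal radiation effect, a rising PSA and a biopsy beyond 2 years, which suggests a deliberately specific endpoint. The protocol also bases intervention for PSA failure on a positive biopsy and/or distant relapse, which may raise uptake. This all stands as a reason to keep the biopsy-proven definition. It does not close the gap, because a man with distant relapse, or with no intervention planned, need not be biopsied. Scheduled 6-monthly visits also end at disease progression, so a later biopsy may not be captured.

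A reader might infer more than the documents support:

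- *That this man never has an event.* He counts for disease-free survival, and for FFBR unless the bounce exception applies.
- *That the curves can only be too favourable.* The bias exists only if unbiopsied lesions include true recurrences.
- *That accepting a biopsy decides his status at any time.* For LF, even a positive biopsy within 2 years may not qualify.
- *That each curve is 8 to 12 points too high.* Rounding control to 51–69%, 24 × 0.31 = 7.4 and 24 × 0.49 = 11.8 PSA failures. Halving for a visible lesion and again for no biopsy leaves 1.9 to 2.9 men, or 8 to 12 points. Neither half is documented for this population, the total pools LF and EPF, and the control rates come from salvage HDR series, not this combined treatment of node-positive men.
- *That an unbiopsied MRI lesion should simply replace biopsy as the main definition, with a negative biopsy clearing it.* Status would still depend on biopsy: a man with a benign lesion is cleared if biopsied and failed if not. It would also bypass the 2-year criterion and the bounce exception.

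**Conclusion.** The point holds as a gap in the definitions, with a conditional bias. Followed as written, true in-prostate recurrences that are not biopsied are lost from FFLF and FFEPF, and censoring does not recover them. The direction is upward if at least one unbiopsied lesion is a true recurrence. The size is unknown: the 4 to 13.5 points at 50% uptake rest on borrowed rates, an assumed low local share and an assumed uptake, and are to be divided between the curves.

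The conflicts in wording need no assumption. LC contradicts itself for this man, EPC tests the wrong site, and the biopsy-only events do not match Section 2.3.3. Because the plan will only describe these secondary endpoints, with no threshold or power attached, this is a worthwhile clarification and not a threat to the trial's main conclusion.

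**What to change.** In Sections 9.1.1 and 12.3:

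1. Keep biopsy-proven LF and EPF as the main definitions.
2. Prespecify a sensitivity analysis of FFLF and FFEPF that also counts an MRI-positive, unbiopsied lesion in a man whose PSA failure meets the FFBR definition, including its bounce exception. Assign the event by site and date it at the MRI.
3. State how the more-than-2-years histologic criterion applies in each version.
4. Report how many men with biochemical recurrence had a suspicious MRI lesion, and how many of those were biopsied.
5. Reconcile LC and EPC with LF, EPF and Section 2.3.3, and make the EPC sentence refer to the gland outside the treated lesion.

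The cost is some definition wording, two counts and one extra analysis, using MRIs already scheduled. No biopsy is mandated and no care changes. The drawback is that some MRI lesions will be false positives, so the second version may overstate failure. That is why both are reported: together they bracket the result for recurrences that MRI can see.
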